3.3.2 Cognitive Measure Outcomes

While we do not necessarily anticipate significant cognitive change within the study's duration, we will apply several robust clinical outcome measures to measure beneficial (or deleterious) effects of treatment, including the MoCA, RBANS, NPI-Q and FAQ.

3.3.3 Safety Measure Outcomes

Classic metabolic, hematologic, and immune blood labs will be collected at Screening, Day 28, and Day 84 Visits and monitored for change following BCG vaccination. Four weeks after the first vaccination, we will assess the first vaccination site and evaluate for any signs of systemic infection prior to second BCG vaccination in the other arm. We will use the FDA Toxicity Grading Scale, as performed in vaccine trials, to denote changes from baseline.

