3 STUDY DESIGN

3.1 Overall Study Design and Plan

This single-site, open-label clinical trial will investigate the immune and neurobiological biomarker effects of BCG vaccination in healthy older adults and older adults with mild cognitive impairment (MCI), and gather data on tolerability, safety and study feasibility. Twenty participants (approx. n=10 cognitively normal, n=10 mild cognitive impairment) will receive two intradermal BCG vaccinations spaced 4 weeks apart and will be evaluated 12 weeks after the initial immunization. Cerebrospinal fluid (CSF) and blood will be collected at Screening (blood only), Baseline, Week 4 (blood only), and Week 12 for to assess safety, IIR and AD biomarkers.

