4.1.2 Exclusion Criteria

Subjects meeting any of the following criteria during the screening evaluation will be excluded:

1. History of chronic infectious disease, such as HIV or untreated or active hepatitis;
2. History of tuberculosis, positive interferon-gamma release assay (IGRA, also known as the QuantiFERON-TB test), including a test with a high reactivity to mycobacteria of non-tuberculosis variety;

3. Prior BCG vaccination, positive T-spot tuberculosis test or a T-spot test showing significant Mycobacteria exposure;
4. A positive SARS-CoV-2 PCR result within 3 months of screening, or known close contact with a confirmed COVID-19 positive person or symptoms highly suspicious for COVID-19 (per CDC guidelines) within 1 month of screening, including fever, cough, shortness of breath, chills, muscle pain, new loss of taste or smell, vomiting or diarrhea, and/or sore throat, based on clinician's judgment;
5. History of treatment with metformin within the past one year;
6. Previous participation (ever) in active immunization research for AD or passive immunotherapy or other disease-modifying treatments for AD within the past three months;
7. Current treatment with immunosuppressants (calcineurin inhibitors, corticosteroids, or biological or cytotoxic immunosuppressants, or disease or condition likely to require high dose steroid or immunosuppressive therapy);
8. Other conditions or treatments associated with increased risk of infections or treatment with immunosuppressive medications for any reason;
9. Current treatment with aspirin > 160 mg/day or chronic, daily NSAIDs;
10. Chronic use of antibiotics;
11. History of keloid formation;
12. Living with someone who is immunosuppressed and/or at high risk for infectious diseases (for example, HIV+ or taking immunosuppressive medications for any reason), or in a job (e.g. healthcare) in which the subject works with immunosuppressed populations;
13. Other/confounding neurological or psychiatric condition, unstable medical or psychiatric conditions, contraindications to BCG use and lab abnormalities or concurrent medication use posing risk for BCG or study procedures;
14. Laboratory abnormalities in B12, Folate, TSH, or other common laboratory parameters that may contribute to cognitive dysfunction;
15. Laboratory abnormalities in CBC, electrolytes, LFTs, BUN, Cr, total serum immunoglobulins, ESR, CRP, or urinalysis posing risk to treatment with BCG per clinician judgment;

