6.2.2 Baseline Visit/BCG Vaccine 1 (Day 1)

All subjects who pass screening will return to MGH CNY for the Baseline visit. At this visit, all baseline clinical measures will be collected, and the first BCG vaccine injection will be administered. The Baseline visit will occur within 28 days of the Screening visit. If necessary, baseline measures may be collected up to 3 days before the Day 1 vaccination visit. The visit will take approximately three hours and will include:

- Vital signs
- Assess any changes to medical history, concomitant medications and/or adverse events
- Neurobehavioral assessments
 - RBANS
 - NPI-Q
- Phlebotomy for biomarker research
- Fasting lumbar puncture for biomarker research
- First BCG vaccine administration followed by 30 minutes of monitoring

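### No safety labs are drawn on Day 1, so lab change after BCG can only be measured from a Screening value up to 28 days before dose 1

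*Combined protocol and SAP*

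**What the plan says.** Section 3.3.3 opens with the lab schedule, "Classic metabolic, hematologic, and immune blood labs will be collected at Screening, Day 28, and Day 84 Visits", and says that these labs are watched for change after vaccination. After a sentence on the vaccination site and signs of systemic infection, it ends: "We will use the FDA Toxicity Grading Scale, as performed in vaccine trials, to denote changes from baseline".

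Footnote 3 of the schedule in section 6.1 defines the safety panel as CBC with differential, CMP, CRP and ESR. The schedule marks it at the Day 28 and Day 84 visits, and the same tests are part of the Screening eligibility labs. The only blood listed for Day 1 in section 6.2.2 is "Phlebotomy for biomarker research". On timing, the same section says "The Baseline visit will occur within 28 days of the Screening visit".

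The Screening labs also decide entry. Exclusion criterion 15 in section 4.1.2 reads: "Laboratory abnormalities in CBC, electrolytes, LFTs, BUN, Cr, total serum immunoglobulins, ESR, CRP, or urinalysis posing risk to treatment with BCG per clinician judgment".

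Under section 5.2 everyone receives active treatment. Section 8.1 plans pre-post paired tests of within-subject change and lists safety among the measures whose change is described. No section says which visit is the baseline for labs.

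**The concern.** In this protocol Baseline is the Day 1 visit, and that visit has no safety-lab values. Any lab change must therefore be taken from Screening, which raises two problems.

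- **Stale reference.** Part of the interval treated as time after BCG may lie before the first injection. A silent rise in CRP or ESR, or a change in the blood count, that arises in that gap looks the same at Day 28 as one that arises after dose 1.
- **Selected reference.** People with concerning Screening labs can be excluded. Those who enter therefore start closer to normal than they would on an unselected day, and chance alone moves some values from normal to abnormal.

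With no control arm, the pre-dose value is the only comparator for lab safety, which falls under a stated secondary objective (section 3.2).

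**Working it through.** **1. Is there really no Day 1 safety draw?** The per-test volumes in section 6.3.1.2 settle this.

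- Screening: 1 + 3 + 5 + 1 + 2 + 6 + 4 + 1 + 1 + 1 = 25 mL.
- Day 28: CBC 3 + CMP 5 + CRP 1 + ESR 2 = 11 mL.
- Day 84: 11 + PT/INR 1 = 12 mL.
- Total: 25 + 11 + 12 = 48 mL, exactly the stated total. Nothing is left for Day 1.

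Section 6.3.1.2 allows a point-of-care CBC and PT/INR before a lumbar puncture, but neither is scheduled at Baseline, and they would not supply CMP, CRP or ESR.

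**2. Share of the interval before any BCG.** Share = gap / (gap + days from dose 1 to the later draw). The gap is at most 28 days (6.2.2). The second visit is 28 to 42 days after dose 1 (6.2.3).

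| Gap (days) | Later draw | Share before BCG |
|---|---|---|
| 7 | Day 28 | 7/35 = 20.0% |
| 14 | Day 28 | 14/42 = 33.3% |
| 21 | Day 28 | 21/49 = 42.9% |
| 28 | Day 28 | 28/56 = 50.0% |
| 28 | Day 28 + 14 | 28/70 = 40.0% |
| 28 | Day 84 | 28/112 = 25.0% |

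Section 6.2.2 also says that "baseline measures may be collected up to 3 days before the Day 1 vaccination visit". If those 3 days are added to the 28, the worst case becomes 31/59 = 52.5%.

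**3. Size of the selection effect, with no BCG effect.** The inputs are assumptions, except the 20 participants (section 3.1): 20 lab values each (400 in all), normal values with a 2.5% out-of-range tail, equal correlation r among Screening, Day 1 and Day 28, and every value in range at Screening. The last is an upper bound, since exclusion is by clinician judgment. Let P2 be the probability that two given visits are both in range, and P3 that all three are.

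- Newly abnormal at Day 28 from Screening: 400 × (0.975 − P2)/0.975. None can resolve.
- Newly abnormal at Day 28 from Day 1: 400 × (P2 − P3)/0.975. By symmetry the same number resolve.

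| r | P2 | P3 | From Screening | From Day 1 | Difference |
|---|---|---|---|---|---|
| 0.50 | 0.95462 | 0.93726 | 8.36 | 7.12 | 1.24 |
| 0.85 | 0.96269 | 0.95422 | 5.05 | 3.48 | 1.57 |

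Section 8.1 gives twelve participants instead of twenty; on that figure all counts scale by 12/20 = 0.6. Because the correlation is equal across visits, the length of the gap has no effect here. The table measures selection only, not staleness.

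**4. Could the Screening-to-Day-1 shift serve as a background rate?** It starts from the same selected value, so under the same assumptions it gives 8.36 (or 5.05) newly abnormal values and none resolving, against 7.12 (or 3.48) from Day 1 to Day 28. It would overstate background and could hide a real effect.

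**The case against.** The Screening sample is a valid pre-dose value, at most about four weeks old by design. The study is an exploratory pilot to which section 8.1 attaches no claims, and one sentence naming Screening as the lab reference would cure the wording. All of this is fair, and it limits the weight of the point. That sentence would not, however, make the reference more recent or remove the selection.

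Several stronger readings are tempting, and the documents do not support them.

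- **Lab toxicity is explicitly graded against a baseline that does not exist.** The grading sentence does not name labs and follows one on the injection site. The other use of the scale, in section 5.4.2, is for local skin reactions. Applying it to labs is reasonable but inferred. The point stands without it, because monitoring for change does name labs.
- **Everything between Screening and Day 1 is charged to BCG.** Adverse events are collected from consent (11.3.1), and medical history, medications and events are reviewed again on Day 1 (6.2.2). Each event gets an onset date and a causality rating (11.3.3, 11.3.4). A recorded infection could be placed before dose 1; only an unrecorded lab shift could not.
- **Flu or COVID-19 vaccination in the gap is a major source of error.** Flu vaccination must be at least 14 days before Baseline (4.1.1, criterion 10), and COVID-19 vaccination within 14 days before Baseline or any BCG dose is excluded (4.1.2, criterion 22). A dose given in the gap is thus at least 14 + 28 = 42 days before a nominal Day 28 draw.
- **Half of the lab change is pre-exposure.** The 50% is a worst-case share of days, not of lab change.
- **Section 3.1 promises Baseline safety labs.** Its sentence, "Cerebrospinal fluid (CSF) and blood will be collected at Screening (blood only), Baseline, Week 4 (blood only), and Week 12 for to assess safety", lists several visits and several purposes jointly and does not assign safety labs to Baseline.

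**Conclusion.** The concern holds in a limited form. The safety panel has no Day 1 value. Its only pre-dose reference may precede dose 1 by 28 days: at worst 50% of the interval to the nominal Day 28 visit, 40% at the end of that window and 25% to Day 84. Typical shares will be lower, and the documents do not give the distribution of gaps. Lab shifts before dose 1 that leave no adverse event record cannot be separated from change after BCG.

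The tilt toward newly abnormal values is modest. A Day 1 reference removes about 1.2 to 1.6 of 5 to 8 such values per 400, under assumed correlations and an upper bound on selection. Its further gain is that worsening and resolving shifts then balance when BCG has no effect. This is a cheap improvement to an uncontrolled descriptive pilot, not a flaw that invalidates its safety data.

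**What to change.** - Add the panel already defined in footnote 3 of section 6.1 to the Day 1 draw, before vaccination. If baseline measures are taken on an earlier day under the 3-day allowance, the reference is at most 3 days old.
- State in sections 3.3.3 and 8.1 that Day 1 is the reference for lab change and for any lab toxicity grading. Keep Screening for eligibility.
- Report worsening and resolving shifts from Day 1 side by side.
- Do not present the Screening-to-Day-1 shift as a background rate, for the reason in step 4 of the working.

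Cost: 11 mL on top of the 60 mL biomarker draw already planned for that visit (6.3.3), so safety blood rises from 48 to 48 + 11 = 59 mL. It also takes one more lab panel per participant and a schedule amendment, but no extra visit or needle stick. If the panel is not added, the protocol should at least name the Screening value as the lab baseline and report each participant's gap to dose 1.

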4 SUBJECT SELECTION

Each Investigator must adhere to the protocol detailed in this document and agree that any changes to the protocol must be approved by Internal Review Board (IRB). Each investigator will be responsible for enrolling only those study subjects who have met protocol eligibility criteria.

4.1 Inclusion/exclusion Criteria

Investigators will use their best clinical judgment when selecting potential research subjects for this study and will not enroll any individuals who are frail or in questionable health, even if they meet all inclusion/exclusion criteria.

4.1.1 Inclusion Criteria

Study subjects meeting all of the following criteria will be allowed to enroll in the study:

1. Individuals between the ages of 55-80;
2. MoCA ≥ 18 ;
3. Normal cognition as defined by MoCA ≥ 26 or MCI as defined by the NIA-AA Workgroup (2011) and MoCA score between 18 and 25 (inclusive);
4. Education level, English language skills and literacy indicates subject will be able to complete all assessments;
5. Ability to provide informed consent;
6. Willing and able to complete all assessment and study procedures, including blood and lumbar punctures, and clinical assessments;
7. If on cholinesterase inhibitor and/or memantine, doses are stable for 3 months prior to baseline;
8. Negative test results for HIV antibody and Tuberculosis (QuantiFERON) at screening;
9. No prior BCG exposure either through birth vaccinations (born in North American) or BCG bladder cancer treatment.
10. Documentation of current flu season vaccination dated at least 14 days prior to baseline visit.

4.1.2 Exclusion Criteria

Subjects meeting any of the following criteria during the screening evaluation will be excluded:

1. History of chronic infectious disease, such as HIV or untreated or active hepatitis;
2. History of tuberculosis, positive interferon-gamma release assay (IGRA, also known as the QuantiFERON-TB test), including a test with a high reactivity to mycobacteria of non-tuberculosis variety;

3. Prior BCG vaccination, positive T-spot tuberculosis test or a T-spot test showing significant Mycobacteria exposure;
4. A positive SARS-CoV-2 PCR result within 3 months of screening, or known close contact with a confirmed COVID-19 positive person or symptoms highly suspicious for COVID-19 (per CDC guidelines) within 1 month of screening, including fever, cough, shortness of breath, chills, muscle pain, new loss of taste or smell, vomiting or diarrhea, and/or sore throat, based on clinician's judgment;
5. History of treatment with metformin within the past one year;
6. Previous participation (ever) in active immunization research for AD or passive immunotherapy or other disease-modifying treatments for AD within the past three months;
7. Current treatment with immunosuppressants (calcineurin inhibitors, corticosteroids, or biological or cytotoxic immunosuppressants, or disease or condition likely to require high dose steroid or immunosuppressive therapy);
8. Other conditions or treatments associated with increased risk of infections or treatment with immunosuppressive medications for any reason;
9. Current treatment with aspirin > 160 mg/day or chronic, daily NSAIDs;
10. Chronic use of antibiotics;
11. History of keloid formation;
12. Living with someone who is immunosuppressed and/or at high risk for infectious diseases (for example, HIV+ or taking immunosuppressive medications for any reason), or in a job (e.g. healthcare) in which the subject works with immunosuppressed populations;
13. Other/confounding neurological or psychiatric condition, unstable medical or psychiatric conditions, contraindications to BCG use and lab abnormalities or concurrent medication use posing risk for BCG or study procedures;
14. Laboratory abnormalities in B12, Folate, TSH, or other common laboratory parameters that may contribute to cognitive dysfunction;
15. Laboratory abnormalities in CBC, electrolytes, LFTs, BUN, Cr, total serum immunoglobulins, ESR, CRP, or urinalysis posing risk to treatment with BCG per clinician judgment;
16. Laboratory abnormalities in PT-INR, which would pose a risk to performing the lumbar puncture procedure;
17. Discontinuation of cholinesterase inhibitor or memantine within one month (28 days) prior to baseline visit;
18. Females who are pregnant, lactating or of child-bearing potential;
19. If male with female partner(s) of childbearing potential, unwilling or unable to adhere to contraception requirements specified in the protocol;
20. Administration of live vaccine < 60 days prior to Baseline;
21. Increased intracranial pressure as determined on a fundoscopy/neurological examination performed within 30 days of LP;
22. COVID-19 vaccination < 14 days prior to baseline or any BCG immunizations.

4.1.2.1 Women of Childbearing Potential (WOCBP)

For the purposes of this study, women of childbearing potential are defined as all women who are capable of becoming pregnant, unless they meet one of the following criteria:

1. 12-months post-menopausal.
2. Post-hysterectomy.
3. Surgically sterile.

If a female subject does not meet these criteria and is considered of childbearing potential, they will be excluded from the clinical trial.

Male subjects with female partners of child-bearing potential must use at least 1 of the following contraceptive methods: hormonal contraceptives (oral, injectable, patch, intrauterine devices), a barrier method (such as condoms or diaphragm) used with a spermicide (a foam, cream, or gel that kills sperm), male sterilization, or total abstinence from heterosexual intercourse, when this is the preferred and usual lifestyle of the subject. Abstinence is defined as refraining from heterosexual intercourse during the entire period of risk associated with the study. Note that periodic abstinence (calendar, symptothermal, post-ovulation methods), withdrawal (coitus interruptus), spermicides only, and lactational amenorrhoea method are not acceptable methods of contraception.

4.2 Recruitment

Up to twenty-six subjects will be screened and enrolled in the study, and after screening we expect twenty subjects to complete the study.

4.2.1 Recruitment of Subjects through Advertising

Advertisement flyers will be posted on bulletin boards around MGB campuses to advertise for the study as well as an advertisement on Partners Rally for Research. A phone number will be provided that will ring directly to the research coordinator, and voice messages can be left for the coordinator on a password-protected voice mailbox. The study coordinator will contact the subject and explain study in further detail and if the subject is interested, potentially complete a telephone prescreening. A listing of the study will also be posted on the MGH ACTRU website.

4.2.2 Recruitment of Subjects from among MGB Providers

Subjects will be recruited from the outpatient clinical practices of the principal investigator ([name]). If the potential subject is the investigator's patient, another member of the study or clinic staff will introduce the study to the patient and determine if they are interested in learning more about the study. An NP investigator will be made available to explain the study to the subject at their request. If the potential subject is not the investigator's patient, the investigators will not directly approach the patient regarding possible participation in the study.

Other providers across MGB will also be made aware of the study (including key eligibility criteria) via email and provided with a link to the Rally ad. These providers (not participating directly in the study) may discuss the study directly with their patients, if they choose to do so. If the prospective participant is interested, their provider will give them a copy of the consent form (unstamped) for review as well as a link to the Rally ad, which contains the research coordinator's contact information.

4.2.2.1 Recruitment of Subjects from the Massachusetts Alzheimer's Disease Research Center

Subjects will also be recruited from an observational study that follows a longitudinal research cohort (LC) of approximately 400 active research participants in the Massachusetts Alzheimer's Disease Research Center (MADRC) recruited from the MGH's Memory Disorders Unit clinic and other diverse sources. LC subjects are followed-up on an approximately annual basis, either in-person at the MGH or by means of a telephone follow-up 'visit'. Study staff will only contact subjects that have indicated to the MADRC that they are interested in hearing about/participating in other studies.

5 SUBJECT ENROLLMENT

5.1 Informed Consent Process

This study will be conducted in compliance with Title 21 Part 50 of the United States of America Code of Federal Regulations (CFR), Federal Regulations, and ICH Guidance Documents pertaining to informed consent.

Potential subjects will be given general information about the research (e.g., through informational sheets, letters, or discussion with their treating physicians). If they are interested in learning more about the study, they will then contact the research coordinator. The research coordinator will obtain verbal consent in accordance with Partner's Prescreening Guidelines prior to performing a telephone prescreening interview. If the subject meets pre-screening criteria and wishes to continue the screening process, an in-person screening visit will be scheduled.

At the screening visit, an investigator will meet with the potential subject to review and discuss the details of the study using the informed consent document as a guide. This discussion will include all the required elements of informed consent, including the purpose of the research, the procedures to be followed, the risks and discomforts, as well as potential benefits associated with participation, and alternative procedures to study participation. Their questions will be answered to their satisfaction. The subject will be provided with adequate time to reflect on the potential benefits and risks and possible discomforts of participation, and to make an informed decision. A licensed Nurse Practitioner Investigator or Physician Investigator will then obtain written informed consent from each participant prior to the initiation of any study procedures. All potential subjects will be given the opportunity to speak with the Physician Investigator should a licensed Nurse Practitioner be involved in obtaining informed consent. While some subjects will have MCI or subjective memory loss, they must be deemed capable of providing informed consent by the Nurse Practitioner or Physician Investigators. Subjects who are not capable of providing informed consent will be excluded from this study.

